3.0 Outcome Measures

3.1 Primary Outcome Measures

- Primary safety will be assessed by the incidence of device related revision, adverse events and metal ion measurements.
- Adverse events will be documented at the intraoperative and all post-operative evaluation intervals. The incidence of surgery-related and device-related events such as squeaking, liner fracture, device revision, malfunction, migration, subluxation, dislocation, loosening, nerve damage, deep infection, deep vein thrombosis, pulmonary embolism, or bone breakage/fracture will also be collected. Any adverse events with an unknown association with the surgery or device will also be collected.
- For both investigational and control subjects, metal ions will be measured in whole blood, including Co, Cr, Ni, Ti, Zr, Nb, Mo, V and aluminum (Al) ion levels, preoperatively, 3 month, 6 month, 1 year, 2 years, 5 years, 7 years and 10 years post-operatively.

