17.1 Definitions for safety reporting

A. Adverse Event (AE)

An AE is any untoward medical occurrence, unintended disease or injury, or untoward clinical signs (including abnormal laboratory findings) in subjects, users or other persons, whether or not related to the investigational medical device (ISO 14155:2011).

This definition includes:

- events related to the investigational medical device or the comparator
- events related to the procedures involved
- a worsening of any conditions previously recorded as part of the medical history assessment

For users or other persons, this definition is restricted to events related to investigational medical devices.

B. Serious Adverse Event (SAE)

A SAE is an adverse event that (ISO 14155:2011):

- led to death,
- led to serious deterioration in the health of the subject, that either resulted in:
 - 1) a life-threatening illness or injury, or
 - 2) a permanent impairment of a body structure or a body function, or
 - 3) in-patient or prolonged hospitalization, or
 - 4) medical or surgical intervention to prevent life-threatening illness or injury or permanent impairment to a body structure or a body function
- led to foetal distress, foetal death or a congenital abnormality or birth defect

Planned hospitalization for a pre-existing condition, or a procedure required by the protocol, without serious deterioration in health, is not considered a serious adverse event.

C. Adverse Device Effect (ADE)

An ADE is an adverse event related to the use of an investigational medical device (ISO 14155:2011).

This definition includes:

- adverse events resulting from insufficient or inadequate instructions for use, deployment, implantation, installation, or operation, or any malfunction of the investigational medical device
- any event resulting from use error or from intentional misuse of the investigational medical device.

D. Serious Adverse Device Effect (SADE)

An SADE is an adverse device effect that has resulted in any of the consequences characteristic of a serious adverse event (ISO 14155:2011).

E. Unanticipated Serious Adverse Device Effect (USADE)

A serious adverse device effect which by its nature, incidence, severity or outcome has not been identified in the current version of the risk analysis report or the clinical investigation plan (ISO 14155:2011, 21 CFR 812).

F. Device Deficiency

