22.4 Adverse Events

Time course distribution of Adverse Events for the safety population will be tabulated. Analysis of revision status will be done using a test of proportion such as Binomial test and Chi-square test unless otherwise noted. Additionally, the safety of R3 ODH-ODH will be assessed by analyzing the revision rate at 6 months, two years, 5 years, 7 years and 10 years post-operatively as well as by applicable operative and post-operative adverse events (device related or otherwise). Kaplan-Meier estimates will be used to analyze the survivorship of the prosthesis. For survivorship analyses, revision of one or more components will be defined as failure.

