#### 6.9.2 Adverse Events

The total number of adverse events of all classifications will be summarised by treatment and overall along with the number and proportion of subjects experiencing an adverse event of any type.

The above will also be summarised by seriousness, severity, relationship to study device/ procedure and outcome.

The frequency of ADEs and SADEs that occurred between each study visit will be presented along with the total for the overall study. The number of subjects recording each will also be presented.

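### The protocol asks for the time course of all adverse events, but the only by-interval table in SAP 6.9.2 covers ADEs and SADEs

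*SAP*

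**What the plan says.** **Protocol.** Section 22.4 states: "Time course distribution of Adverse Events for the safety population will be tabulated". Section 22.3.3 carries the same sentence. Neither limits it by relatedness. Section 17.1 A defines an adverse event as an untoward occurrence "whether or not related to the investigational medical device (ISO 14155:2011"), and it expressly includes events related to the comparator and to the procedures. Section 3.1 makes adverse events part of the primary safety outcome, names surgery-related as well as device-related events, and adds: "Any adverse events with an unknown association with the surgery or device will also be collected".

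**SAP.** Section 6.9.2 plans three things:
- total adverse events of every kind, with the number and proportion of subjects affected, by treatment and overall;
- the same broken down by seriousness, severity, relationship to device or procedure, and outcome;
- one table with a time dimension: "The frequency of ADEs and SADEs that occurred between each study visit will be presented", plus the study total and the number of subjects.

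The terms in that last table are defined in Protocol 17.1 C and D: "An ADE is an adverse event related to the use of an investigational medical device (ISO 14155:2011"), and "An SADE is an adverse device effect that has resulted in any of the consequences characteristic of a serious adverse event (ISO 14155:2011").

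**The concern.** Adverse events are a primary endpoint, and the extension exists to judge long-term safety of a new bearing out to 10 years. Protocol 18.0 itself separates short-term from longer-term causes of failure, and Protocol 24.3 says that pseudotumor risk with this device is unknown and is to be monitored partly through adverse event capture. Timing is therefore part of what the safety data are meant to show.

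Under SAP 6.9.2, whether an event enters the time course depends on its being judged related to the investigational device. A late event of uncertain cause, or one put down to the original operation, would be counted in the whole-study total without appearing in any interval. Early complications attributed only to surgery would likewise be absent from the early intervals. The SAP gives no reason for narrowing what the protocol states twice.

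**Working it through.** No formula applies and the plan states no figure to reproduce. The check is a comparison of scope.

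1. *Protocol time course* (22.3.3, 22.4): adverse events as defined in 17.1 A, so all of them, in the safety population.
2. *SAP time course* (6.9.2): ADEs and SADEs. Because an SADE is a serious ADE, naming both adds nothing outside the ADE set. An SAE that is not device-related is in neither.
3. *Event classes side by side:*

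| Event class | Protocol time course | SAP interval table | SAP whole-study summaries |
|---|---|---|---|
| ADE, serious or not | yes | yes | yes |
| AE or SAE attributed solely to the procedure | yes | no | yes |
| Unrelated AE or SAE | yes | no | yes |
| AE of unknown association | yes | not stated; no, unless classed as an ADE | yes |
| Any AE in a control subject | yes, if controls are in the safety population | no, read literally | yes, by treatment |

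4. *The procedure row.* The exclusion is limited to events attributed to the procedure alone. The ADE definition takes in "adverse events resulting from insufficient or inadequate instructions for use, deployment, implantation, installation, or operation", and also use error, so some implantation events are ADEs.
5. *The control row.* Controls receive commercially available components (Protocol 4.2), while an ADE is defined by use of an investigational device. Five of the 25 enrolled subjects are controls. That they belong in the safety population is taken from SAP 6.9 and 6.9.2, which analyse primary endpoints in that population and split adverse events by treatment.
6. *What a corrected table must allow for.* In the schedule of assessments the intervals after discharge run from about 3 months (3 to 6 months) to 3 years (2 to 5 years). That is 36 ÷ 3 = 12 times as long, so raw counts per interval are not comparable without the number followed. Revised subjects are withdrawn (Protocol 18.0) and entry to the extension is by fresh consent (Protocol 2.0), so that number changes. Control events up to 2 years are collected retrospectively, if consented and available (Protocol 2.0).

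**The case against.** The strongest reply is that little is lost. The study has 25 subjects and its adverse event reporting is descriptive. Protocol 22.3.1 allows data to be shown in tables or listings, and 22.3.3 requires a listing of everything. Analyses at 5, 7 and 10 years would also let a reader difference successive all-event totals. The SAP Introduction names table shells that are not among the documents and might hold an all-event interval table.

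Part of this stands. Differencing would give some timing, if the summaries are repeated at each cut. But after year 5 it gives two windows (5 to 7 and 7 to 10 years) where the visit schedule gives five, and counts of subjects with an event cannot be differenced when a subject has events in both windows. The general permission to use listings does not displace two specific sentences that call for a tabulation. If the shells do hold the table, the SAP text should say so.

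Some stronger readings are tempting and are not supported:
- *That the omitted events disappear from the analysis.* They remain in the totals, the relationship breakdown and the listing.
- *That the protocol's time-course sentence itself says related or not.* The phrase "applicable operative and post-operative adverse events (device related or otherwise") comes from a later sentence of 22.4 on the overall safety assessment. The point rests on the unrestricted term and its definition in 17.1.
- *That all surgery-related and all unknown-association events drop out.* Some implantation events are ADEs, and neither document says how unknown relationship is classed.
- *That a given share of events loses its timing.* Neither document gives an expected number of events or a device-related share. Counting the named events in Protocol 3.1 that could occur with any hip replacement does not help either: the general list in Protocol 24.1 also includes revision, squeaking, loosening and dislocation, so it does not separate the classes.

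**Conclusion.** The mismatch is real. Followed as written, SAP 6.9.2 does not deliver a tabulation that the protocol promises twice for a primary endpoint. What is missing is the by-interval timing of adverse events outside the ADE set, and of control-group events on a literal reading. It is not the events themselves. No numerical size can be derived from the documents.

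The conclusion assumes that the SAP text governs and that no unseen table shell already fills the gap. It also assumes that unknown-association events are not silently treated as ADEs; if they are, that one class is covered and the rest of the point is unchanged. Because the table is descriptive, no test or estimate elsewhere in the SAP is affected. The departure is worth correcting because the protocol is clear and the remedy is cheap.

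**What to change.** Replace the interval sentence in SAP 6.9.2 with text to this effect:

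> For each interval between study visits and overall, by treatment and in total, in the safety population, the number of events and the number of subjects with at least one event will be tabulated for: any AE; any SAE; procedure-related AEs; AEs of unknown relationship; ADEs; SADEs. The number of subjects followed in each interval will be shown. Control-group AEs up to 2 years will be marked as retrospectively collected.

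State also how an unknown relationship is classed, and whether the ADE label is applied to control devices. If the sponsor prefers to keep the narrower table, the SAP should record and justify the departure from Protocol 22.3.3 and 22.4.

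The cost is SAP wording and extra rows and columns in one table. No new data are needed: the planned ADE table already requires event timing, and relationship is already summarised. The small downside is a longer descriptive table.

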#### 6.9.3 Metal Ion Analysis

Metal ion levels (Co, Cr, Ni, Ti, Zr, Nb, Mo, V and Al) will be summarised as a continuous variable at 6 months, 2 years, 5 years, 7 years and 10 years post-operatively.

As well as the summary above, the proportion of subjects with each metal ion level  $\geq$  7 parts per billion (ppb) will be presented at each study visit.

### 6.10 Analysis of Secondary Endpoint(s)

All secondary endpoints are assessed primarily using the ITT population and the PP population will be used for a secondary analysis.

The analysis of HHS and HOOS will be performed on observed data as well as with LOCF imputed data.

Statistical Analysis Plan	
A Consecutive Series Pilot Study Evaluating the Safety and Effectiveness of a New Hard-on-Hard Total Hip Replacement System in Patients with Non-inflammatory Arthritis with a Standard THA Metal Ion Control Group	Number: 2011-ODHH166
	ST: 1040
	Version: V1.0 26-Nov-2018
	Page: 12 of 13

#### 6.10.1 The Harris Hip Score (HHS)

Where HHS data has been collected it will be summarised using descriptive statistics at baseline, 6-months, 2 years, 5 years, 7 years and 10 years visits by treatment and overall.

The change from baseline in HHS score as derived in section 6.4 will also be summarised at the same study visits by treatment and overall.

Paired t-tests will be used to test for a difference in the change from baseline HHS score for each treatment separately from baseline to 5-years, 7-years and 10-years. The differences will be presented along with the associated 95% confidence intervals. If the assumptions of the t-test is violated then the Wilcoxon signed rank test will be used instead with Hodges-Lehmann estimates of the median difference and 95% confidence interval reported.

A sensitivity analysis will be carried out in the same way as described above however using the data as it is recorded without LOCF methods applied.

#### 6.10.2 Hip Disability and Osteoarthritis Outcome Scores (HOOS)

HOOS consists of 5 subscales; pain, other symptoms, function in daily living, function in sport and recreation, and hip related quality of life. Five possible responses are allowed for each question and each answer equates to a score of 0 to 4. Points equating to the responses for each subcategory are added together and normalized to a maximum total score of 100.

Where HOOS data has been collected the subscales will be summarised using descriptive statistics at baseline, 6-months, 2 years, 5 years, 7 years and 10 years visits by treatment and overall.

The change from baseline in HOOS subscale scores as derived in section 6.4 will also be summarised at the same study visits by treatment and overall.

Statistical Analysis Plan	
A Consecutive Series Pilot Study Evaluating the Safety and Effectiveness of a New Hard-on-Hard Total Hip Replacement System in Patients with Non-inflammatory Arthritis with a Standard THA Metal Ion Control Group	Number: 2011-ODHH166 ST: 1040
	Version: V1.0 26-Nov-2018
	Page: 13 of 13

Paired t-tests will be used to test for a difference in the change from HOOS subscale scores for each treatment separately from baseline to 5-years, 7-years and 10-years. The differences will be presented along with the associated 95% confidence intervals. If the assumptions of the t-test is violated then the Wilcoxon signed rank test will be used instead with Hodges-Lehmann estimates of the median difference and 95% confidence interval reported.

A sensitivity analysis will be carried out in the same way as described above however using the data as it is recorded without LOCF methods applied.

#### 6.10.3 Radiographic Success

Radiographic findings including the assessment of bone loss, radiolucencies, subsidence, and heterotopic ossification as compared to the preoperative radiograph will be summarised by treatment and overall at baseline, 6-months, 2 years, 5 years, 7 years and 10 years.

#### 6.10.4 Health Economic Data

The following health economic data will be summarised by treatment and overall:

- Surgical blood loss
- Length of hospital stay
- Operative time
- Re-hospitalizations
